### **12.2.3 Analysis of the Pharmacokinetic Endpoints**

The planned analyses will be described in more detail in the statistical analysis plan (SAP).

The serum pharmacokinetic (PK) concentration profiles will be graphically presented. The PK endpoints will be derived from the individual serum HM15211 profiles during the elimination phase using the non-compartmental models.  $C_{trough}$  will be derived from the pre-dosing PK samples on Day 78. The PK parameters will be summarized by dose.

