## 5.0 STUDY OBJECTIVES

### 5.1.1 Primary Objectives and Endpoints

To assess safety and tolerability of HM15211 after administration of multiple SC doses in obese subjects with NAFLD by:

- Incidence of adverse events (AEs) (cardiovascular [CV] events, rash/inflammatory dermatitis and other skin disorders, gastrointestinal [GI] events, and gallstone formation [cholelithiasis] will be managed following separate AE guidance document)
- Incidence of clinical lab abnormalities (including serum amylase, serum lipase, coagulation, thyroid stimulating hormone (TSH), serum calcitonin)
- Immunogenicity (Anti-drug antibodies [ADAbs], neutralizing antibodies [nAbs], anti-polyethylene glycol antibodies [anti-PEG])
- Incidence and severity of clinical findings on physical examination
- Change from baseline in vital signs (blood pressure [BP], heart rate [HR], respiratory rate, and temperature]);  
BP assessed by 24-hour ambulatory blood pressure monitoring (ABPM);  
HR assessed by 24-hour ambulatory electrocardiography monitoring (Holter ECG; central reader)
- Change from baseline in 12-lead ECG parameters; the primary ECG endpoint will be QTcF
- Injection site reactions

To assess the pharmacokinetic (PK) profile of HM15211 after administration of multiple SC doses in obese subjects with NAFLD by, but not limited to:

- Maximum concentration ( $C_{\max}$ )
- Time to reach  $C_{\max}$  ( $t_{\max}$ )
- Trough plasma concentration ( $C_{\text{trough}}$ )
- Area under the concentration-time curve (AUC), eg,  $AUC_{0-t}$  at steady state
- Terminal elimination rate constant ( $k_{\text{el}}$ )
- Terminal half-life ( $t_{1/2}$ )
- Apparent clearance (CL/F)
- Apparent volume of distribution ( $V_z/F$ )

To assess a reduction of liver fat after administration of multiple doses in obese subjects with NAFLD by:

- Absolute and % changes of fat on magnetic resonance imaging-estimated proton density fat fraction (MRI-PDFF)

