#### In-house Period 2:

Day 77: Subjects will check in to the clinic in the morning on Day 77 for a 5-day In-house Period. They will receive standardized meals throughout their inpatient stay. Subjects will be connected to an ABPM system, and overnight measurements will be taken to familiarize the subjects with the device. ABPM measurements will continue throughout Day 82.

Day 78 to 82: In the morning of Day 78, subjects will get connected to a Holter ECG for 24-hour measurements and will continue these until Day 82. Sample for the assessment

of PK will be collected pre-dose for  $PK_{trough}$ . Study drug will be administered. Measurements of vital signs, sampling for PK, sampling for laboratory parameters and evaluations for safety parameters will be performed as stated in the SOE

Subjects will continue to stay in-house for safety evaluations and PK. They will be disconnected from Holter monitoring and ABPM on Day 82 and will be released home in the morning of Day 82, after the PK sample has been collected.

For subjects participating in cohort 1-3, the in-house stay until day 82 is optional. These subjects will continue to stay in-house for safety evaluations, PD and PK until Day 81, after they are disconnected from Holter monitoring and ABPM.

Subjects will undergo an MRI/MRI-PDFF assessment to assess liver fat during week 12, as close as possible to Day 85. For subjects in cohort 1-5 and up, visceral fat will be assessed additionally during the imaging procedure.

Outpatient Visits:

Subjects will return to the CRU during elimination phase of the drug on Days 85 and 99. On Day 85, measurements of vital signs, sampling for laboratory parameters including incretins/metabolic hormones, lipid profiles and particles, amino acid panel, bone metabolism parameters, glucose metabolism parameters, inflammatory markers, ketone bodies, local injection site evaluation, and evaluations for safety parameters will be performed for the assessment after 12 weeks of dosing. For subjects in cohort 1-4 and up, a FibroScan assessment will be performed additionally, as stated in the SOE.

On Day 99, sampling for PK, PD and safety will be performed as stated in the SOE.

Follow-up Visit:

A Follow-up Visit will be performed on Day 113 ( $\pm 2$ ) to collect final safety assessments and the last PK sample. Please see [Table 16-1](#) Schedule of Events for details.

Sampling and Assessment:

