### 9.1.16 Pharmacokinetic Assessments and Schedule

Blood for PK analysis of the study drugs will be collected at the time points indicated in the [Table 16-1](#) Schedule of Events and follow the PK sampling schedule [Table 9-3](#). One 2-mL sample per scheduled time point will be collected to provide a minimum of 500 µL of serum for PK measurements and 500 µL of serum as a secondary back-up sample. Instructions for sample processing and shipment will be provided in the PK Sample and Shipping Instructions. Pre-dose sampling will be taken within 10 minutes before dosing. Dosing should occur at approximately 08:00 h on every dosing day. The actual time of PK sampling should not deviate from the nominal time by more than  $\pm$  5 minutes during the Inpatient Period, and by more than  $\pm$  2 days for the Elimination Period and Follow-up Visit. If Visit during elimination period or follow-up visits will be performed on a different day, the time point for the sampling will still be in the morning, preferably at the same time (at approximately 08:00h). The actual time of dosing, actual sampling dates and times should be recorded.

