**Table 9-3 PK Sampling Schedule for cohorts 1-1 and 1-2**

| PK sampling schedule          |         |         |                                     |
|-------------------------------|---------|---------|-------------------------------------|
| Treatment Period              | Week 1  | Day 1   | Pre-dose 1 st dosing     |
|                               |         |         | 8 h after 1 st dosing    |
|                               | Day 2   |         | 24 h after 1 st dosing   |
|                               |         | Day 3   | 48 h after 1 st dosing   |
|                               | Day 4   |         | 72 h after 1 st dosing   |
|                               | Week 2  | Day 8   | Pre-dose 2 nd dosing     |
|                               |         | Day 10  | 48 h after 2 nd dosing   |
|                               | Week 3  | Day 15  | Pre-dose 3 rd dosing     |
|                               | Week 4  | Day 22  | Pre-dose 4 th dosing     |
|                               | Week 5  | Day 29  | Pre-dose 5 th dosing     |
|                               | Week 6  | Day 36  | Pre-dose 6 th dosing     |
|                               | Week 8  | Day 50  | Pre-dose 8 th dosing     |
|                               | Week 9  | Day 57  | Pre-dose 9 th dosing     |
|                               | Week 12 | Day 78  | Pre-dose 12 th dosing    |
|                               |         | Day 80  | 48 h after 12 th dosing  |
|                               |         | Day 81  | 72 h after 12 th dosing  |
| Elimination Period ( $\pm$ 2) | Week 13 | Day 85  | 168 h after 12 th dosing |
|                               | Week 15 | Day 99  | 504 h after 12 th dosing |
| F/U ( $\pm$ 2)                | Week 17 | Day 113 | 840 h after 12 th dosing |

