**Table 9-4 PK Sampling Schedule starting from cohort 1-3**

| PK sampling schedule    |          |         |                                     |
|-------------------------|----------|---------|-------------------------------------|
| Treatment Period        | Week 1   | Day 1   | Pre-dose 1 st dosing     |
|                         |          |         | 8 h after 1 st dosing    |
|                         |          | Day 2   | 24 h after 1 st dosing   |
|                         |          | Day 3   | 48 h after 1 st dosing   |
|                         |          | Day 4   | 72 h after 1 st dosing   |
|                         |          | Day 5*  | 96 h after 1 st dosing   |
|                         | Week 2   | Day 8   | Pre-dose 2 nd dosing     |
|                         |          | Day 10  | 48 h after 2 nd dosing   |
|                         | Week 3   | Day 15  | Pre-dose 3 rd dosing     |
|                         | Week 4   | Day 22  | Pre-dose 4 th dosing     |
|                         | Week 5   | Day 29  | Pre-dose 5 th dosing     |
|                         | Week 6   | Day 36  | Pre-dose 6 th dosing     |
|                         | Week 8   | Day 50  | Pre-dose 8 th dosing     |
|                         | Week 9   | Day 57  | Pre-dose 9 th dosing     |
| Week 12                 | Day 78   |         | Pre-dose 12 th dosing    |
|                         |          |         | 8 h after 12 th dosing   |
|                         |          | Day 79  | 24 h after 12 th dosing  |
|                         |          | Day 80  | 48 h after 12 th dosing  |
|                         |          | Day 81  | 72 h after 12 th dosing  |
|                         | Day 82** |         | 96 h after 12 th dosing  |
| Elimination Period (±2) | Week 13  | Day 85  | 168 h after 12 th dosing |
|                         | Week 15  | Day 99  | 504 h after 12 th dosing |
| F/U (±2)                | Week 17  | Day 113 | 840 h after 12 th dosing |

\*Sampling on Day 5 will start with Cohort 1-4 and will not be taken for cohort 1-3.

\*\* Sampling on Day 82 will be optional for cohort 1-3 but will be taken in cohort 1-4.

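### Section 12.2.3 takes the PK endpoints from the elimination phase (Days 85 and 99), which cannot yield the primary Cmax, tmax or steady-state AUC

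*Protocol*

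**What the plan says.** Section 12.2.3 gives one rule for all PK parameters: "The PK endpoints will be derived from the individual serum HM15211 profiles during the elimination phase using the non-compartmental models". It makes one exception, for Ctrough, which "will be derived from the pre-dosing PK samples on Day 78".

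The protocol uses the same term in Section 6.2, and identically in the Study Summary: "Subjects will return to the CRU during elimination phase of the drug on Days 85 and 99". Tables 9-3 and 9-4 put those two samples under an Elimination Period heading. The first is listed as "168 h after 12 th dosing" and the second falls at 504 h. The Day 113 sample (840 h) has its own follow-up label, and Section 9.1.16 also separates the two when it sets the sampling tolerance at ± "2 days for the Elimination Period and Follow-up Visit". The week-1 profile and every sample from 8 to 96 h after dose 12 are listed under Treatment Period.

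Section 5.1.1 lists Cmax, tmax, AUC (with AUC0-t at steady state as the example), kel, t1/2, CL/F and Vz/F as primary PK endpoints. Table 12-1 repeats them.

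**The concern.** A peak, its time and the area over a dosing interval have to come from samples taken within that interval. The window named in 12.2.3 starts where the last dosing interval nominally ends. An analyst who follows the sentence cannot produce several primary endpoints. One who sets it aside departs from the protocol and chooses the profile outside it.

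The choice has consequences here. Section 4.4 bases the exposure margin on steady-state weekly AUC, approximated by single-dose AUCinf. The week-12 AUC0-168 is the direct check on that approximation. Section 8.6 also allows unblinding and analysis cohort by cohort, so one stated rule is needed for all cohorts.

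**Working it through.** **Step 1. Samples after dose 12, by the protocol's own labels (Tables 9-3 and 9-4)**

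| Cohorts | Treatment Period | Elimination Period | Follow-up |
|---|---|---|---|
| 1-1, 1-2 | pre-dose, 48, 72 h | 168, 504 h | 840 h |
| 1-3 and up | pre-dose, 8, 24, 48, 72, 96 h (96 h optional in 1-3) | 168, 504 h | 840 h |

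The elimination window holds two samples, or three if follow-up is counted.

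**Step 2. What each endpoint needs**

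- Cmax and tmax need the peak region of a dosing interval. From the elimination samples, Cmax becomes the Day 85 concentration and tmax the Day 85 time. With ±2 days that is 168 − 48 = 120 h to 168 + 48 = 216 h.
- AUC0-168 at steady state needs samples from 0 to 168 h. At nominal times the window supplies only the right-hand endpoint, so there is nothing to integrate.
- CL/F = dose / AUC0-168 at steady state, so it fails with the AUC. Vz/F = (CL/F) / kel fails with it.
- kel and t1/2 can be formed: kel = ln(C at 168 h / C at 504 h) / 336 h, t1/2 = ln 2 / kel. Two points leave no residual degree of freedom.

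No other passage assigns a profile to these parameters.

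**Step 3. Illustration of size**

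The protocol gives no human half-life or tmax. I assumed a one-compartment model with first-order input and 12 weekly doses. Half-life was 35.7, 60 or 86.0 h (the ends are the animal range in Section 4.3) and single-dose tmax was 24, 48 or 72 h (assumed).

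- ke = ln 2 / half-life; ka solves ln(ka/ke)/(ka − ke) = tmax.
- C(t) after dose 12 is proportional to the sum over i = 0 to 11 of [ka/(ka − ke)] × [exp(−ke(t + 168i)) − exp(−ka(t + 168i))].
- AUC from a schedule is the linear trapezoid: the sum of (C_j + C_j+1)/2 × (t_j+1 − t_j).

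Example: half-life 35.7 h gives ke = 0.693/35.7 = 0.0194 per h. With tmax 24 h, ka = 0.0766 per h and the 168 h value is 0.081 of Cmax. The other extreme, 86.0 h with tmax 72 h, gives 0.576. The 35.7/72 pair requires ka below ke, but it sets none of the extremes for the Day 85 concentration or for observed Cmax.

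| Quantity | Range over the nine scenarios |
|---|---|
| Day 85 concentration / true Cmax, at 168 h | 0.081–0.576 |
| Same, sampled at 120 h | 0.205–0.784 |
| Same, sampled at 216 h | 0.032–0.406 |

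A separate run with half-lives of 36–168 h and tmax of 48–96 h gave 0.27–0.76 at 168 h.

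**Step 4. What the dose-12 interval would give**

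| Schedule within the interval | AUC / true AUC0-168 | Observed / true Cmax |
|---|---|---|
| Table 9-4 in full (0, 8, 24, 48, 72, 96, 168 h) | 0.995–1.005 | 0.989–1.000 |
| Table 9-4 without 96 h | 0.988–1.054 | 0.989–1.000 |
| Table 9-3 (0, 48, 72, 168 h) | 0.829–0.967 | 0.778–0.998 |

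On the Table 9-3 schedule the observed tmax is 48 h in every scenario. If the Day 85 sample falls at 120 or 216 h and the AUC is not brought to 168 h, the full Table 9-4 schedule gives 0.763–0.899 or 1.092–1.173 of AUC0-168.

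**The case against.** The strongest reply is that the term is never formally defined. Section 6.2 says when two visits fall; it does not say the phase consists of those days alone. The tables use the word Period, not phase. On a looser reading, everything after the last dose, the endpoints can be derived. The rest of the protocol points to that intent: Section 5.1.1 asks for AUC at steady state, Section 4.4 speaks of weekly AUC, and Amendment 3 added samples after dose 12, which its log entry places around Tmax. Section 12.2.3 defers detail to the SAP, the study is descriptive, and no sample is lost.

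Much of this stands. The looser reading is the likely intent, and the literal analysis is unlikely to be run. But that reading conflicts with the protocol's own labels and leaves open whether week-1 Cmax and tmax are endpoints. Deferral to the SAP covers missing detail; it does not repair a stated rule that names the wrong window.

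The simulation rests on assumed values, and the finding does not need it. It is also fair to say that the replacement text goes beyond the minimum, and that the sparse dose-12 sampling in cohorts 1-1 and 1-2 is a separate matter from the quoted sentence. Finally, kel and t1/2 from Days 85 and 99 alone would be weak: in the same model the Day 99 concentration is about 0.1–7% of Day 85, and Day 113 at most about 0.5%.

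**Conclusion.** The concern holds. As written, 12.2.3 makes the primary Cmax and tmax wrong, and leaves AUC over the steady-state dosing interval, CL/F and Vz/F without data. Only Ctrough (by its exception), kel and t1/2 survive. This follows from the sampling labels and needs no model. The size, with Day 85 at 8–58% of true Cmax at the nominal time, is illustrative and depends on animal half-lives and an assumed tmax. The error is in the analysis text, not in the sampling design, and it should be corrected before the PK analysis.

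**What to change.** Replace the sentence in 12.2.3 with:

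> PK parameters will be derived by non-compartmental analysis using actual times: week-1 Cmax and tmax from Days 1–8; Cmax, tmax and AUC0-168 at steady state from the dose-12 interval (Day 78 pre-dose to Day 85), interpolated or extrapolated to 168 h when the Day 85 sample is off nominal time; CL/F from the dose-12 AUC0-168; kel and t1/2 from the terminal samples through Day 113; Vz/F from both.

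Add:

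> Cohorts 1-1 and 1-2 have only pre-dose, 48, 72 and 168 h samples in the dose-12 interval, so their week-12 Cmax, tmax and AUC are coarse and will be marked as such.

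The essential part is assigning Cmax, tmax, AUC0-168 and CL/F to the dose-12 interval. The week-1 parameters, the off-nominal rule and the cohort note could instead go in the SAP.

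The cost is two sentences, carried into the SAP, with no new samples or procedures. The change cannot supply the 8, 24 and 96 h samples that cohorts 1-1 and 1-2 lack after dose 12.

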|  |  | 
optional for subjects that are already participating in cohort 1-3.
 
Section 2.0 Study Summary, 6.2 Study Description, Section 16.0 Appendix A in Table 16-3 Table 16-4
 
5. Extension of ABPM and Holter monitoring Period
 
Due to the added PK sampling timepoints around <math>T_{max}</math>, a consecutive extension of ABPM and Holter monitoring until Day 5 in week 1 and until Day 82 in week 12 will be added.
 
Section 2.0 Study Summary, 6.2 Study Description, section 9.1.6 Vital signs, section 9.1.11 ECG Procedure, Section 9.1.14 ABPM, Section 16.0 Appendix A in Table 16-3 and Table 16-4
 
6. Adjustment of ECG timepoint
 
Due to the extended ABPM and Holter monitoring period until Day 5 and Day 82, the ECG measurements are moved from Day 4 to Day 5 and from Day 81 to Day 82 as well, as they are supposed to be conducted after the ambulatory devices have been removed.
 
Section 9.1.11 ECG Procedure, Section 16.0 Appendix A in Table 16-2, 16-3 and 16-4
 
7. Part 2 of the study will not be conducted
 
Description of Part 2 and language referring to Study Part 2, will be deleted. Language in other parts of the protocol will be adjusted to reflect the changes, such as subject number, etc. As there is only one study part left, the specification "Part 1" will be deleted.
 
Title of the study, section 2.0 Study Summary, section 4.2 Rationale for the Proposed Study, section 4.5 Dose Escalation Algorithm, section 5.0 Study Objectives Part 2, 6.1 Study Design, 6.2 Study Description, 6.3 Rationale for Study Design and Endpoints, 7.0 Part 2 Inclusion and Exclusion Criteria, 8.6 Randomization and Blinding, 9.1.8 Procedures for Clinical Laboratory Samples, 9.1.17 Laboratory Pharmacodynamic Assessments, 9.1.18 MRI-
 |
|--|--|--|

|  |  |  |
|--|--|--|

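### By-dose summaries of 12th-dose Cmax, tmax and AUC are confounded with the sampling grid, because the two lowest-dose cohorts have no 8, 24 or 96 h sample

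*Protocol*

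**What the plan says.** Section 5.1.1 lists Cmax, tmax and AUC among the primary PK endpoints, the last as "Area under the concentration-time curve (AUC), eg, $AUC_{0-t}$ at steady state". Section 12.2.3 obtains the parameters from each subject's serum profile by non-compartmental methods, takes Ctrough from the Day 78 pre-dose sample, and closes with "The PK parameters will be summarized by dose". It does not mention that the sampling schedule differs between cohorts.

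The schedule does differ. Table 9-3 ("PK Sampling Schedule for cohorts 1-1 and 1-2") has "48 h after 12 th dosing" as the first sample after the last dose. Table 9-4 ("PK Sampling Schedule starting from cohort 1-3") adds an 8 h sample and one at "24 h after 12 th dosing", and also 96 h, with the footnote "Sampling on Day 82 will be optional for cohort 1-3 but will be taken in cohort 1-4". Within the 168 h interval after dose 12 this gives:

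| Cohort (Table 4-1 dose) | Times after dose 12 (h) |
|---|---|
| 1-1, 1-2 (0.01, 0.02 mg/kg) | 0, 48, 72, 168 |
| 1-3 (0.04 mg/kg) | 0, 8, 24, 48, 72, (96 optional), 168 |
| 1-4 and up (0.06 mg/kg and later doses) | 0, 8, 24, 48, 72, 96, 168 |

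After the first dose all cohorts share 0, 8, 24, 48, 72 and 168 h; the 96 h sample is taken from cohort 1-4 on.

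**The concern.** Each cohort is one dose level, so the step from the sparse to the rich week-12 grid falls exactly between 0.02 and 0.04 mg/kg. Non-compartmental Cmax and tmax are read off the samples taken, and AUC is built from them. On the sparse grid the two samples between pre-dose and the end of the interval are at 48 and 72 h, so steady-state tmax can hardly be anything else, and one straight line bridges the first 48 h.

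The sparse times are a subset of the rich ones. For the same profile, sparse-grid Cmax can equal the rich-grid value or fall below it, never exceed it. If the curve rises and bends over within 48 h, the straight line also misses area. Both effects lower the two smallest doses, so exactly proportional exposure would look more than proportional from 0.02 to 0.04 mg/kg. At stake are the reported steady-state exposure and any conclusion about proportionality drawn from the by-dose table.

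**Working it through.** **Sample count.** Table 9-3 has 19 samples and Table 9-4 has 23. The four extra are 96 h after dose 1 and 8, 24 and 96 h after dose 12.

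**Inputs.** Dosing interval τ = 168 h (weekly dosing, section 6.1). The protocol states no human half-life or tmax. Assumed: half-life 35.7 h (lowest animal value in section 4.3; the highest is 86.0 h) up to 168 h, and single-dose tmax 24 to 96 h. The model is one compartment with first-order absorption at steady state, without assay error.

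**Formulas.** ke = ln 2 / half-life. ka solves ln(ka/ke)/(ka − ke) = single-dose tmax. For unit dose and volume,

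C(t) = ka/(ka − ke) × [e^(−ke·t)/(1 − e^(−ke·τ)) − e^(−ka·t)/(1 − e^(−ka·τ))],

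and the true AUC over the interval is 1/ke. Observed AUC is the linear trapezoid over the sample times; observed Cmax is the largest sampled value.

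**Worked case: half-life 35.7 h, tmax 24 h.** ke = 0.01942 and ka = 0.0766 per hour. C(0) = C(168) = 0.053, C(48) = 0.515, C(72) = 0.339. Sparse-grid AUC = 48 × (0.053 + 0.515)/2 + 24 × (0.515 + 0.339)/2 + 96 × (0.339 + 0.053)/2 = 13.6 + 10.2 + 18.8, or about 42.7. True AUC = 1/0.01942 = 51.5. Ratio 0.829. The true peak is 0.661, so the Cmax ratio is 0.515/0.661 = 0.778.

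**Observed value as a fraction of truth, range over half-lives 35.7 to 168 h:**

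| Single-dose tmax | AUC, sparse grid | AUC, rich grid without 96 h | AUC, rich grid with 96 h | Cmax, sparse grid | Cmax, rich grid |
|---|---|---|---|---|---|
| 24 h | 0.829–0.933 | 1.000–1.054 | 0.997–1.005 | 0.778–0.913 | 0.995–1.000 |
| 36 h | 0.920–0.950 | 1.001–1.043 | 0.997–1.008 | 0.944–0.957 | 0.955–0.997 |
| 48 h | 0.947–0.963 | 1.000–1.014 | 0.997–1.002 | 0.985–0.994 | same as sparse |
| 72 h | 0.963–0.976 | 0.988–0.994 | 0.995–0.997 | 0.997–1.000 | same as sparse |
| 96 h | 0.973–0.980 | 0.984–0.990 | 0.994–0.996 | 0.993–0.996 | same as sparse |

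Sparse-grid AUC is low in every case. For Cmax, both grids miss a little of the peak when tmax is 48 h or later, so without error the two grids then agree exactly. Between-subject spread leaves a small gap: with log-SD 0.5 on ka and 0.25 on ke, and typical half-lives of 60 and 86 h, the sparse-to-rich geometric mean ratio for Cmax was 0.84–0.87 at a typical tmax of 24 h, 0.93–0.94 at 36 h, 0.98 at 48 h and about 1.00 at 72 h.

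**Effect on proportionality.** Suppose the true AUC ratio from 0.02 to 0.04 mg/kg is 2.0. In the worst case with the 96 h sample it would appear as 2.0 × 1.005/0.829 = 2.42; without it, 2.0 × 1.054/0.829 = 2.54. With tmax at 48 h or later and the 96 h sample taken, the range is 2.0 × 0.996/0.980 = 2.03 to 2.0 × 1.002/0.947 = 2.12.

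**The case against.** **The detail belongs in the SAP.** Section 12.2.3 says the SAP will give more detail, and the SAP is not at hand. It could restrict comparisons to common times. That stands as a possibility. But the protocol itself fixes both the unequal grids and an unqualified by-dose summary, and followed as written these bias a comparison of primary PK endpoints.

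**No proportionality test is planned.** True: section 6.3 excludes hypothesis testing and the summary is descriptive. Readers will still compare columns set side by side by dose.

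**Cmax and tmax are not explicitly tied to dose 12.** Also true: only AUC (as an example) and Ctrough are. The point therefore concerns any Cmax, tmax or AUC that is taken at steady state.

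**The large figures need an early peak.** This stands. The amendment log in section 1.3 extends monitoring to Days 5 and 82, the 96 h days, with the reason "Due to the added PK sampling timepoints around" Tmax. That hints at a later peak but does not settle it, since 8 and 24 h samples were added at week 12 as well. With 9 active subjects per dose and an assumed between-subject CV of 30%, the 95% interval for a two-dose geometric mean ratio spans a factor of exp(2.12 × 0.294 × √(2/9)) = 1.34 either way, so a 2 to 5% AUC shift would be well inside the noise.

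**Schedule changes between cohorts are allowed.** Sections 4.5 and 9.1.16 do allow them. That discloses the grid change but does not make the resulting parameters comparable.

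**A stronger reading.** One might infer that the artefact steers dose escalation. The documents do not support this. Section 4.5 sets the decision after 2 to 4 weeks of treatment, on available PK data and modelling. A cohort's own week-12 samples do not exist then, and first-dose grids match through 72 h. An earlier cohort's week-12 data, or the optional review when a cohort is complete, could contribute, but they are not the main input.

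**Conclusion.** The point holds. Any 12th-dose Cmax, tmax or AUC summarised by dose under section 12.2.3 is confounded with the sampling grid, and the two lowest doses are the ones disadvantaged. Under the assumed profiles their AUC0-168 is 0.83 to 0.98 of truth, with the loss near the small end if tmax is 48 h or later. A material loss of Cmax needs a tmax clearly before 48 h, and a general claim that Cmax is substantially understated would go beyond the documents. All sizes rest on the assumed half-life, tmax, one-compartment form and linear trapezoid; the subset argument for Cmax and the limited choice of tmax do not. Ctrough is unaffected, and the 168, 504 and 840 h samples are common to all cohorts. The consequence is for reported steady-state exposure and its reading across 0.02 to 0.04 mg/kg. The change is worth making because it is cheap and the endpoints are primary.

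**What to change.** Add to section 12.2.3:

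- Cross-dose comparison of 12th-dose Cmax and AUC uses the times common to all cohorts: pre-dose, 48, 72 and 168 h.
- First-dose comparisons use 0, 8, 24, 48, 72 and 168 h, leaving out the 96 h sample taken from cohort 1-4 on.
- Week-12 parameters from all available samples are reported separately for cohorts 1-3 and up, showing which cohort 1-3 subjects have the 96 h sample. These values, tmax in particular, are marked as not comparable with cohorts 1-1 and 1-2.

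Cohort 1-3 needs its own marking because leaving out 96 h can move its AUC from 1.005 to 1.054 of truth in the worst case above.

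The cost is a second non-compartmental run on existing data and a few lines of text; no new samples are needed. The downside is that common-grid AUC is somewhat low in every cohort and common-grid tmax is uninformative, so these values serve only for comparison between doses. A population PK model would be an acceptable alternative.
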